Emerging evidence suggests that hypotension and OH may be associated with progressive cognitive decline with advancing age [49]. Cross-sectional analysis of more than 3000 participants in the Honolulu-Asia Aging Study found poorer cognitive performance in individuals with SBP < 110 mmHg compared to those with normal and high BP [50]. Cognitive deficits associated with chronic asymptomatic hypotension include: slowed cognitive speed, fewer word recall, decreased accuracy of response, limited attention, prolonged reaction times and reduced memory and concentration capacity [51-53]. In addition, several investigations have documented a link between asymptomatic OH and cognitive deficits [54-57], and poor test performance on tasks of recent recall and sustained attention and processing speed was evident in middle-aged subjects with asymptomatic OH compared to subjects without OH after adjustment for age [58]. The proposed association between hypotension, OH and cognitive deficits relates to chronic cerebral hypoperfusion and significantly reduced CBFv has been reported in otherwise healthy asymptomatic hypotensive subjects compared to age-matched normotensive subjects [52]. Further, Laboratory evidence suggests that elevation in BP improves CBFv and cognitive performance in healthy subjects, in post-acute stroke patients and in subjects with SCI. [8, 9, 59-61] We recently demonstrated a direct association between increases in BP and increased CBFv, [62, 63] and note a relationship between CBFv and cognitive performance in persons with SCI. [10, 11]

Operational Definitions:

There is a general lack of consensus regarding the definition of hypotension, as well as whether chronic hypotension exists, [64] or is a problem. [30, 65] In 1978, the World Health Organization (WHO) defined hypotension as a SBP \leq 110 mmHg for males and \leq 100 mmHg for females, without regard to diastolic BP (DBP).[66] However, much of the literature on hypotension is equivocal regarding the definition. Large epidemiological studies discuss

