double-blind, placebo-controlled trial. Preliminary data on the mean seated SBP response to midodrine compared to placebo is presented in 21 hypotensive subjects with SCI (Figure 1). The results suggest significantly elevated SBP following midodrine (10 mg) administration compared to the other 3 conditions; however, individuals responses to midodrine varied significantly (Figure 2). In fact only one-third of the subjects tested (7 subjects) responded to midodrine with a normal SBP (between red dashed lines); 7 remained hypotensive and 7 had hypertensive responses. Furthermore, compared to placebo (Figure 3A), the percentage of SBP recordings reflecting systolic hypertension (i.e., ≥ 140 mmHg) following midodrine administration (Figure 3B) was significantly increased ($p<0.01$) over the 4-hour observation, whereas the percent of normotensive SBP observations was unchanged. Collectively these data suggest that midodrine is effective at normalizing SBP in some hypotensive individuals with SCI, but resulted in seated systolic hypertension in one-third of the population tested.

Droxidopa is a prodrug that is converted to NE, which binds to alpha-receptors and causes increases in orthostatic BP. We have demonstrated that 400 mg oral administration of droxidopa significantly increases seated SBP in hypotensive individuals with SCI; however, individual responses varied. [16] The proportion of SBP recordings within the normotensive range (i.e., 111-139 mmHg) did not differ from the no-drug trial (**Figure 4A**) following administration of either the 100 mg (**Figure 4B**) or 200 mg (**Figure 4C**) dose of droxidopa; however, the 400 mg dose (**Figure 4D**) did appear to increase the proportion of normal SBP recordings ($42.3 \pm 28.5\%$) over a 3-hour seated observation compared to the no-drug ($19.3 \pm 29.5\%$), 100 mg ($11.8 \pm 23.3\%$) and 200 mg ($18.9 \pm 21.8\%$) trials, although this difference was not statistically significant. Three individuals each had a single recording of a seated SBP ≥ 140 mmHg (156, 150, 149 mmHg), which was observed during the first 30-minutes, and constituted 3% of all observed SBP recordings (**Figure 4D**). Individual seated SBP responses (mmHg) to droxidopa, averaged over the 3-hour observation, is presented (**Figure 5**). As depicted (**Figure 5A**), 5 individuals responded to the 400 mg dose with a SBP \geq

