significantly increased in those who responded to the 400 mg dose of droxidopa compared to the non-responders (105 ± 10 vs. 81 ± 10 mmHg, respectively; $p=0.0048$), and although the magnitude of effect was doubled in the non-responders, the SBP response did not differ significantly (9.0 ± 10 vs. 18.6 ± 16 mmHg, respectively; $p=0.2937$). These data suggest that individuals with a seated SBP below 95 mmHg may need a higher dose of droxidopa to normalize SBP.

d) Research Design and Methods

We propose to determine the dose of droxidopa that normalizes seated SBP in hypotensive individuals with SCI, and to determine the effect of that dose of droxidopa on supine BP, orthostatic BP and CBFv compared to placebo.

Study Population: Fifty subjects with SCI will be screened for study eligibility. We anticipate that approximately 40 of the subjects screened will be eligible and will undergo the dose optimization trial (**Study 1**). We anticipate that 25 subjects will respond to droxidopa with a normal seated SBP, and these individuals will be eligible for the randomized placebo-controlled trial to determine the effect of the optimal dose on supine BP, orthostatic BP and CBFv compared to placebo (**Study 2**). Each subject will be randomized by the Research Pharmacy to receive either droxidopa/placebo or placebo/droxidopa for the placebo-controlled prospective trial. Randomization will occur in a double-blinded manner. Study medication and placebo will be distributed by the James J Peters VAMC Pharmacy Service. The study is proposed to be completed in two years. Total enrollment will be accomplished within 18 months of obtaining full IRB approval, which should be complete within 6 months of funding, and subject participation is estimated to last about 6-8 weeks. A complete description of the study population can be found in the Human Subjects Form 11.

Study Procedures: Identical testing procedures will be performed at the JJP VAMC and the ISMMS according to the table below.

Procedures Table	Screening	Study 1									Study 2	
		1	2	3	4	5	6	7	8	9	10	11
Visit												
Medical Intake	X											
Medical History	X											
OH Survey	X											
AD Survey	X											
Seated BP	X	X	X	X	X	X	X	X	X	X	X	
Supine BP	X										X	X
HUT BP											X	X
CBFv											X	X
Side-effects		X	X	X	X	X	X	X	X	X	X	X
OH Symptoms Survey											X	X
Fatigue Survey	X										X	X

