Screening Visit – Individuals with SCI will be approached by investigators and asked to provide informed consent to participate in a screening study to determine eligibility. Compression garments will be removed, if tolerated, prior to assessment of supine and seated BP.

Any subject taking a vasoconstrictor agent will be asked to stop these medications 2 days or 5 half-lives (whichever is longer) prior to the screening visit, if medically cleared. The screening assessments will include: medical intake information (Appendix 1), medical history (Appendix 2), physical examination, American Spinal Cord Injury Impairment Scale (AIS) classification (if not assessed in the prior 6-months), clinical symptoms survey for OH and AD (Appendix 3) and

brachial BP assessment, recorded one time per minute for 10 minutes while in the seated and supine positions. Individuals will be eligible to participate in the study if 1) the average seated BP meets the WHO definition of hypotension (i.e., SBP \leq 110 mmHg for males or SBP \leq 100 mmHg for females) or 2) there is evidence of OH (i.e., orthostatic fall in BP \geq 20/10 mmHg when moved from the supine to the seated position) and 3) there is no evidence of sustained elevation in BP \geq 140/100 mmHg in either the supine or seated positions. This visit will take about 2 hours.

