PART II

A Research Protocol must be submitted with this application.

A. LAY RESEARCH SUMMARY

Provide 1-2 paragraphs explaining the Research in lay terms, including the specific study aim, any important background information to explain why the research is important, what will be done, and how results will be analyzed.

The goal of this study is to determine the efficacy of the drug Droxidopa (Northera) in increasing blood pressure in subject with hypotension, low blood pressure, which is classified as blood pressure less than 110/70 in males and 100/70 in females. The first aim is to determine the proportion of subject with SCI who have a normotensive response to Droxidopa. The second is to determine the proportion of subject with SCHI who express a hypertensive response to Droxidopa. A Normal blood pressure ranges from 111-139 in males and 101-139 in females and a hypertensive blood pressure is anything higher than 140 in males and females.

The study would take place in James J. Peters VA Medical Center (JJPVAMC), The Icahn School of Medicine at Mount Sinai (ISMMS) in Manhattan, New York and The Kessler Foundation (KF) at the Kessler Institute for Rehabilitation in West Orange, NJ.

B. PROTOCOL SUMMARY

A. Provide a brief (200-250 word) summary of background information for physician/scientistsList total # of subjects approved for enrollment by the IRB.
List total number of subjects enrolled (Signed a consent form) over the life of this study. List total number of subjects enrolled(Signed a consent form) in the current approval period. List total number of subjects terminated from study (Lost to follow-up, terminated by PI, withdrew consent, etc.). List total number of subjects that have completed all study tasks/procedures and follow-up visits. List total number of subjects currently receiving study treatment or participating in study activities.:

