d. Justify any exclusion of specific gender, age, and racial or ethnic groups:

N/A

6. State inclusion criteria for enrollment in study:

Study 1:

- 1) Male or Female, age 18 to 89 with traumatic SCI.
- 2) SCI Subjects (n=40):
 - a) Any level of injury;
 - b) Any AIS grade of SCI;

- c) Non-ventilator dependent
- d) Primarily wheelchair dependent for mobility;
- e) Duration of injury < 1 year

3) Low Blood Pressure:

Systolic BP less than 110 mmHg and/or diastolic BP less than 70 mmHg for males;
Systolic BP less than 100 mmHg and/or diastolic BP less than 70 mmHg for females;

4) Primary Language is English.

Able to provide informed consent

Study 2:

5) Male or Female, age 18 to 89 with traumatic SCI.

6) SCI Subjects (n=40):

- a) Any level of injury;
- b) Any AIS grade of SCI;
- c) Non-ventilator dependent
- d) Primarily wheelchair dependent for mobility;
- e) Duration of injury < 1 year

7) Low Blood Pressure:

Systolic BP less than 110 mmHg and/or diastolic BP less than 70 mmHg for males;
Systolic BP less than 100 mmHg and/or diastolic BP less than 70 mmHg for females;

8) Primary Language is English.

Able to provide informed consent

9) Showed a normotensive blood pressure in response to Droxidopa during study 1.

7. State exclusion criteria for enrollment in study:

Study 1 and Study 2:

- Current illness or infection
- Individuals with frequent or severe autonomic dysreflexia
 - a. More than 3 symptomatic events per week
 - b. BP \geq 140/90 mmHg
 - c. Significant adverse subjective symptoms reporting
- Hypertension
- Any neurological condition other than SCI (Alzheimer's disease, dementia, stroke, multiple sclerosis, Parkinson's disease, etc.)
- History of epilepsy or other seizure disorder
- History of traumatic brain injury (TBI)
- Liver or kidney disease
- Bladder problems including blockage of the urine and/or weak urine stream.
- Diagnosis of a psychiatric disorder such as schizophrenia or bipolar disorder
- Known artery disease, heart failure, AV block, and irregular heartbeat
- Any allergies to droxidopa, aspirin, polyethylene oxide, polyethylene glycol, hydroxypropyl cellulose, butylated hydroxytoluene, magnesium stearate, hypromellose, yellow ferric oxide, and red ferric oxide
- Major surgery in the last 30 days
- Illicit drug abuse in the past 6 months
- Pregnant
- Your prescription medications will be reviewed by the study investigators and research staff.

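### Aim 1.1 counts a participant as normalized on post-dose SBP alone, and the entry criteria can admit people whose seated SBP is already in the success range

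*Combined protocol and SAP*

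**What the plan says.** **Endpoint.** In the Protocol (Study 1 and Data Analysis, Aim 1.1) and in item 17 of the Combined protocol and SAP, success is a mean SBP at 60-120 minutes of 111-139 mmHg in men or 101-139 mmHg in women. Neither document adds a condition on pre-dose SBP, a minimum rise or a no-drug comparison. The Aim 1.1 wording in the Protocol's Specific Aims and in the Combined document's statement of purpose adds a further clause: reaching the 800 mg maximum without adequate response.

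**Entry.** There are three different texts.
- Protocol, Screening Visit: average seated SBP at or below 110 (men) or 100 (women), or alternatively "there is evidence of OH (i.e., orthostatic fall in BP" of at least 20/10 mmHg from supine to seated. Sustained BP at or above 140/100 is barred "in either the supine or seated positions".
- Combined document, item 6: "Systolic BP less than 110 mmHg and/or diastolic BP less than 70 mmHg for males", with 100 and 70 for women. OH is not mentioned.
- Combined document, Lay Research Summary: hypotension, "which is classified as blood pressure less than 110/70 in males and 100/70 in females".

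The Protocol's Operational Definitions give the hypotension definition "without regard to diastolic BP".

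**Use.** Research Design and Methods states the goal as finding "the dose of droxidopa that normalizes seated SBP in hypotensive individuals with SCI". Data Analysis offers the H1.1 proportion as the first estimate of the drug's normalizing effect, and says the results will be used to power a larger trial. Only those counted as normotensive go on to Study 2.

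**The concern.** A level reached after dosing shows normalization only if the person was below that level before. Someone who enters already in range can be counted at the first dose, have that dose taken as optimal and qualify for Study 2, with no demonstrated drug effect. Study 1 has no control arm to reveal this.

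At stake is the main product of this unpowered pilot: a proportion described as a drug effect in hypotensive people. In-range entrants raise it whenever they are counted more often than low-SBP entrants are.

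The Protocol's Preliminary Data show that level and effect can part. Seated recordings in range made up 19.3% with no drug, 18.9% at 200 mg and 42.3% at 400 mg, "over a 3-hour seated observation compared to the no-drug" and lower-dose trials; the difference was not statistically significant. These are shares of recordings, not of participants. Of the ten people given 400 mg, those who reached the range rose by 9.0 mmHg and those who did not by 18.6. The Protocol remarks that "the magnitude of effect was doubled in the non-responders", although the difference was not significant (p=0.2937).

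**Working it through.** The plan gives no figure for this point to reproduce; it states that the analyses are not powered.

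**1. Overlap between entry and success.**
- Diastolic route (Combined document, item 6): SBP is unrestricted apart from the exclusion of hypertension. Entry SBP can lie anywhere in 111-139 (men) or 101-139 (women), which is the whole success range.
- OH route (Protocol, Screening Visit): supine SBP at most 139, minus a fall of at least 20, gives seated SBP of at most 119. The overlap is 111-119 (men) or 101-119 (women). If a diastolic fall of 10 alone counts as OH, which the text leaves open, the overlap again reaches 139.
- Both texts applied together: a man going from 138/80 supine to 115/65 seated meets the Protocol by OH and the Combined document by diastolic BP, and is already in range. Joint application narrows the gap but does not close it.

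**2. How often an in-range man is counted with no drug effect.** Assume normal visit values, within-person visit SD of 5-12 mmHg (not in the documents), and limits 110.5-139.5.

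| True seated SBP | In range at one visit |
|---|---|
| 112 | 0.54-0.62 |
| 115 | 0.63-0.82 |
| 119 | 0.72-0.96 |
| 125 | 0.77-1.00 |

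From 200 to 800 mg in 100 mg steps there are seven dose levels. Let a be P(in range) and b be P(below range). With independent visits, stopping uncounted if above range, the chance of ever being counted is a(1 − b^7)/(1 − b). Over the four SBP values this is 0.87-1.00. I use s = 0.8 to 1.0.

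**3. Effect on the proportion.** Let f be the share entering in range and r the counted rate among low-SBP entrants. Then the observed p = f·s + (1 − f)·r, so r = (p − f·s)/(1 − f). For p = 0.60:
- f = 10%: (0.60 − 0.10)/0.90 = 55.6% with s = 1.0; (0.60 − 0.08)/0.90 = 57.8% with s = 0.8.
- f = 20%: (0.60 − 0.20)/0.80 = 50.0%; (0.60 − 0.16)/0.80 = 55.0%.
- f = 30%: (0.60 − 0.30)/0.70 = 42.9%; (0.60 − 0.24)/0.70 = 51.4%.

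Both f and s are assumptions.

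**4. Chance counting among low-SBP entrants.** Even r is not purely drug effect. A simulation with no drug effect, screening SBP at or below 110 and seven independent visits counted 12.8-36.3% at least once (visit SD 5-12). It assumed a true mean of 93 (midpoint of the 105 and 81 mmHg in Preliminary Data) and SD of √(10² + 12²) = 15.6. Means of 88 to 98 give 9-45%. The source is ten people, and the sentence giving 105 and 81 is cut in the text, so this is only a rough guide.

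**5. The 800 mg clause.** Read literally, the two aims statements class a participant who reaches the maximum dose without adequate response as normotensive. The Study 1 text lists the same event as a separate reason to stop, and both analysis sections leave it out. The definitions contradict each other.

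**The case against.** The diastolic route appears only in the Combined document, an application form that is to be accompanied by a research protocol, and the Protocol's screening text does not contain it. Under that text a man at 125/65 without OH is not eligible. This stands: the 125/65 case is possible under one of two conflicting texts and cannot be taken as certain. The narrower OH overlap remains under the Protocol alone.

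Including people with OH is evidently deliberate, since the Protocol addresses hypotension and OH together. That is a reason to report them by entry route, not to drop them.

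Two stronger inferences are tempting.
- A reader might infer that in-range entrants are what would make H1.1 succeed. The exact 95% CI includes 60% for 18-30 of 40 or 28-43 of 60. If 40% of low-SBP entrants are counted, support has probability 31% (n=40) or 18% (n=60) with f = 0, and 70-85% or 63-83% with f = 20%. That contrast assumes no chance counting among low-SBP entrants. Suppose instead that 40% truly respond and step 4's rates apply to the other 60%. The counted rate at f = 0 is then 0.4 + 0.6 × 0.128 = 0.477 to 0.4 + 0.6 × 0.363 = 0.618, and support is already about 69-96% or 61-95%. At the upper rate, in-range entrants lower support, because the counted proportion moves above 60%. The documents cannot settle which case applies.
- A reader might infer that Study 2 is biased. It compares droxidopa with placebo within each person, so in-range entrants change whom the result describes but do not bias the contrast.

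The 800 mg clause is probably a misplaced stopping rule, and the analysis sections are clean. It is a wording defect, but in the definition of a primary endpoint.

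**Conclusion.** The point holds as a gap in the endpoint definition. Aim 1.1 measures a post-dose level, not a change of state, and neither entry text guarantees that participants start below that level. The bias in the estimated normalizing effect is upward as long as in-range entrants are counted more often than low-SBP entrants.

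The existence of the gap follows from the text. Its size does not, because the share of in-range entrants is not given. Under the illustration of 20% in range with 80-100% of them counted, an observed 60% corresponds to 50-55% among low-SBP entrants, an overstatement of 5-10 percentage points. With 10% in range it is about 2-4 points. No claim is made about how often the H1.1 rule would be met. The plan should be corrected before analysis, but the trial is not invalidated.

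**What to change.** 1. State that pre-dose seated SBP is recorded at each Study 1 visit. The Home Monitoring text already refers to baseline levels. For H1.1, report the proportion moving from below range pre-dose to in range at 60-120 minutes, together with the change from pre-dose SBP. Show participants who were in range before the dose as their own category. State that visit-to-visit noise remains, because Study 1 has no control.
2. Base the H1.1 numerator and denominator on participants whose screening seated SBP is at or below 110 (men) or 100 (women), the Protocol's own limits. Report OH-only and diastolic-only entrants separately. This step alone does not remove the chance counting in step 4 of the working, which is why the transition analysis leads.
3. Delete the 800 mg clause from the Aim 1.1 endpoint definition in the Protocol's Specific Aims and in the Combined document's statement of purpose. The Study 1 escalation and stopping rules are untouched.
4. Reconcile the three entry texts: the Protocol's Screening Visit, and the Combined document's item 6 and Lay Research Summary.

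The cost is wording and one explicit reading per visit. The H1.1 denominator shrinks: at a 50% rate with 20% set aside, the exact 95% CI goes from 33.8-66.2% (20/40) to 31.9-68.1% (16/32), or from 36.8-63.2% (30/60) to 35.2-64.8% (24/48). The reported response rate will probably be lower.
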